--	--

	
6. Completed a full course (two doses) of a COVID-19 mRNA vaccine after start of glatiramer acetate or interferon
 
7. Received two dose mRNA COVID-19 vaccine (Pfizer or Moderna vaccine) <math>\geq</math> 2 weeks ago
 
8. If the patient has received the mRNA booster, then the mRNA booster should be <math>\geq</math> 2 weeks prior to enrollment
 
9. Total serum immunoglobulin IgG <math>\geq</math> 400 mg/dl at Screening
 
Patients eligible for inclusion in Cohort 6 of this study must fulfill the following criteria:
 
 
1. Signed informed consent must be obtained prior to participation in the study
 
2. Age 18-55 years old at Screening
 
3. Diagnosis of relapsing MS by 2017 revised McDonald criteria
 
4. Must be willing to comply with the study schedule
 
5. Currently on commercially prescribed ofatumumab
 
6. Completed a full course (two doses) of a COVID-19 mRNA vaccine at least <math>\geq</math> 4 weeks after start of commercially prescribed ofatumumab for the treatment of RMS
 
7. Received two dose mRNA COVID-19 vaccine (Pfizer or Moderna vaccine) <math>\geq</math> 2 weeks ago
 
8. Pre-ofatumumab serologies with Hepatitis B testing not indicative of active or latent infection
 
9. Total serum immunoglobulin IgG <math>\geq</math> 400 mg/dl at Screening
 
10. Has received an mRNA booster <math>\geq</math> 2 weeks prior to enrollment
 

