## 2.1 Primary estimands

The estimand is the precise description of the treatment effect and reflects strategies to address events occurring during the trial conduct which could impact the interpretation of the trial results (e.g., premature discontinuation of treatment).

The primary clinical question of interest is: Do relapsing MS participants who receive ofatumumab treatment mount an immune response to non-live mRNA COVID-19 vaccine?

The justification for the primary estimand is that it will capture whether ofatumumab treated participants generate antibodies to mRNA COVID-19 vaccines.

The primary estimand is described by the following attributes:

- **Population:** Defined through appropriate inclusion/exclusion criteria to reflect the targeted population. Relapsing MS participants subdivided into 6 cohorts. (1) Will receive a full course (two doses) of a COVID-19 mRNA vaccine two weeks prior to starting ofatumumab 20 mg subcutaneous treatment; (2) Will receive a full course (two doses) of a COVID-19 mRNA vaccine after at least 4 weeks of commercial ofatumumab 20 mg subcutaneous treatment (3) Will receive a full course (two doses) of a COVID-19 mRNA vaccine after at least 4 weeks of interferon or glatiramer acetate treatment (4) Completed a full course (two doses) of a COVID-19 mRNA vaccine after at least 4 weeks of commercial ofatumumab 20 mg subcutaneous treatment but has not yet received a COVID-19 mRNA booster (5) Completed a full course (two doses) of a COVID-19 mRNA vaccine after at least 4 weeks of interferon or glatiramer acetate (may or may not have received at least 1 COVID-19 mRNA booster) (6) Completed a full course (two doses) of a COVID-19 mRNA vaccine after at least 4 weeks of commercial ofatumumab 20 mg subcutaneous treatment and received at least 1 additional booster vaccine  $\geq$  14 days prior to Screening.
- **Variable:** Achieving immune response as defined by a positive SARS-CoV-2 qualitative IgG antibody assay  $\geq$  14 days after full course (two doses) vaccination (yes/no)
- **Treatment of interest:** Non-live COVID-19 mRNA vaccine either two weeks prior to ofatumumab start or at least 4 weeks after ofatumumab start or while on interferon or glatiramer acetate
- **Intercurrent event:** Discontinuation of treatment/study, or death
- **Summary measure:** Proportion of participants achieving immune response

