5. Completed a full course (two doses) of a COVID-19 mRNA vaccine at least  $\geq 4$  weeks after start of commercially prescribed ofatumumab for the treatment of RMS
6. Currently on commercially prescribed ofatumumab for  $\geq 4$  weeks for the treatment of RMS
7. Received two dose mRNA COVID-19 vaccine (Pfizer or Moderna vaccine)  $\geq 2$  weeks ago
8. Pre-ofatumumab serologies with Hepatitis B testing not indicative of active or latent infection
9. Total serum immunoglobulin IgG  $\geq 400$  mg/dl at Screening

Patients eligible for inclusion in Cohort 5 of this study must meet **all** of the following criteria:

1. Signed informed consent must be obtained prior to participation in the study
2. Age 18-55 years old at Screening
3. Diagnosis of relapsing MS by 2017 revised McDonald criteria
4. Must be willing to comply with the study schedule
5. Currently on commercially prescribed interferon or glatiramer acetate for  $\geq 4$  weeks for the treatment of RMS
6. Completed a full course (two doses) of a COVID-19 mRNA vaccine after start of glatiramer acetate or interferon
7. Received two dose mRNA COVID-19 vaccine (Pfizer or Moderna vaccine)  $\geq 2$  weeks ago
8. If the patient has received the mRNA booster, then the mRNA booster should be  $\geq 2$  weeks prior to enrollment.
9. Total serum immunoglobulin IgG  $\geq 400$  mg/dl at Screening

Patients eligible for inclusion in Cohort 6 of this study must meet **all** of the following criteria:

1. Signed informed consent must be obtained prior to participation in the study
2. Age 18-55 years old at Screening
3. Diagnosis of relapsing MS by 2017 revised McDonald criteria
4. Must be willing to comply with the study schedule
5. Currently on commercially prescribed ofatumumab for  $\geq 4$  weeks for the treatment of RMS

6. Completed a full course (two doses) of a COVID-19 mRNA vaccine at least  $\geq$  4 weeks after start of commercially prescribed ofatumumab for the treatment of RMS
7. Received two dose mRNA COVID-19 vaccine (Pfizer or Moderna vaccine)  $\geq$  2 weeks ago
8. Pre-ofatumumab serologies with Hepatitis B testing not indicative of active or latent infection
9. Total serum immunoglobulin IgG  $\geq$  400 mg/dl at Screening
10. Has received an mRNA booster  $\geq$  2 weeks prior to enrollment

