## 5.2 Exclusion criteria

Participants meeting any of the following criteria are not eligible for inclusion in this study:

1. Already has received the J&J vaccine.
2. Has a contraindication to receiving an mRNA COVID-19 vaccine
3. Has an immediate allergic reaction to past vaccine or injection
4. Any safety finding including low immunoglobulin IgG and/or low immunoglobulin IgM levels requiring an ofatumumab treatment interruption within the 12 weeks immediately prior to vaccination as determined by the HCP
5. Any major episode of infection requiring hospitalization or treatment with intravenous antibiotics within 4 weeks prior to the first vaccination visit or oral antibiotics within two weeks prior to the first vaccination visit
6. Prior treatment with B-cell targeted therapies (e.g., rituximab or ocrelizumab), alemtuzumab, anti-CD4, cladribine, cyclophosphamide, mitoxantrone, azathioprine, mycophenolate mofetil, cyclosporine, methotrexate, total body irradiation, or bone marrow transplantation
7. Prior treatment with S1P agent within 2 months at Screening
8. Prior treatment with natalizumab within 6 months of study enrollment
9. Since commercially prescribed ofatumumab is being used in the study, contraindications as per the USPI will be adhered to which include active infection hepatitis B infection, progressive multifocal leukoencephalopathy and pregnancy.
10. Participation in another interventional clinical trial within 14 days before enrollment.
11. Use of other investigational drugs at the time of enrollment (Screening) or within the prior 30 days, or five elimination half-lives, or until the expected pharmacodynamic effect has returned to baseline, whichever is longer.
12. History of hypersensitivity to any of the study treatments or its excipients or to drugs of similar chemical classes.
13. Have been treated with any of the medications listed below within the time specified:

Medication	Exclusionary if used within the timeframe specified below
Intravenous, oral, intra-articular or intramuscular corticosteroids, adrenocorticotropic hormone	30 days prior to Screening

Medication	Exclusionary if used within the timeframe specified below
Immunosuppressive, chemotherapeutic medications (e.g. mitoxantrone, cyclophosphamide, cladribine, S1P modulators)	2 months prior to first study drug administration
Natalizumab	Within 6 months of study enrollment/Visit 2

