### **6.1.3 Treatment cohorts**

- Cohort 1: RMS participants receiving non-live COVID-19 mRNA vaccine at least two weeks prior to ofatumumab start.
- Cohort 2: RMS participants receiving non-live COVID-19 mRNA vaccine at least 4 weeks after ofatumumab start.
- Cohort 3: RMS participants receiving non-live COVID-19 mRNA vaccine at least 4 weeks after start of prescribed interferon or glatiramer acetate.
- Cohort 4: RMS participants having completed a full course (2 doses) of a non-live COVID-19 mRNA vaccine  $\geq$  4 weeks after ofatumumab start.
- Cohort 5: RMS participants having completed a full course (2 doses) of a non-live COVID-19 mRNA vaccine  $\geq$  4 weeks after glatiramer acetate or interferon start.
- Cohort 6: RMS participants having completed a full course (2 doses) of a non-live COVID-19 mRNA vaccine  $\geq$  4 weeks after ofatumumab start and having received a booster  $\geq$  14 days prior to screening

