Cohort 2: Relapsing MS participants receiving a full course (2 doses) of a non-live COVID-19 mRNA vaccine ≥4 weeks after ofatumumab start.

Will continue taking their prescribed ofatumumab as per their current dosing schedule.

Cohort 3: Relapsing MS participants receiving a full course (2 doses) of a non-live COVID-19 mRNA vaccine ≥4 weeks after start of prescribed interferon or glatiramer acetate.

Will continue administration of their prescribed interferon or glatiramer acetate as per their current dosing schedule.

Cohort 4: Relapsing MS participants having completed a full course (2 doses) of a non-live COVID-19 mRNA vaccine ≥4 weeks after ofatumumab start.

Will continue taking their prescribed ofatumumab as per their current dosing schedule.

Cohort 5: Relapsing MS participants having completed a full course (2 doses) of a non-live COVID-19 mRNA vaccine ≥4 weeks after glatiramer acetate or interferon start.

Will continue taking their prescribed glatiramer acetate or interferon as per their current dosing schedule.

Cohort 6: Relapsing MS participants having completed a full course (2 doses) of a non-live COVID-19 mRNA vaccine ≥4 weeks after ofatumumab start and having received a booster ≥14 days prior to screening.

Will continue taking their prescribed ofatumumab as per their current dosing schedule.

Study completion

According to the protocol, study completion is defined as when the last participant completes the end of study (EOS) visit. Participants who discontinue study treatment or who decide they do not wish to participate in the study further should NOT be considered withdrawn from the study UNLESS they withdraw their consent. Where possible, they should return for the EOS visit.

Study design schematics for Cohorts 1, 2 and 3 are shown in Figures 1, 2, 3 and 4. Study design schematics for Cohorts 4, 5 and 6 are shown in Figures 5 and 6.

Figure 1 Study Design (Cohort 1, Pfizer)

[figure not shown]

Figure 2 Study Design (Cohort 1, Moderna)

[figure not shown]

Figure 3 Study Design (Cohorts 2 and 3, Pfizer)

[figure not shown]

Figure 4 Study Design (Cohorts 2 and 3, Moderna)

[figure not shown]

Figure 5 Study Design (Cohorts 4, 5 and 6, Pfizer)

[figure not shown]
[figure not shown]

Figure 6 Study Design (Cohorts 4, 5 and 6, Moderna)

Primary analysis time point

The primary analysis time point is Visit 4 for Cohorts 1, 2 and 3, and Visit 2 for Cohorts 4, 5 and 6.

Interim analysis

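### Cohort 5's entry criterion omits the 4 weeks on interferon or glatiramer acetate that its estimand population requires, so participants outside that population can count in the reference rate

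*Protocol*

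**What the plan says.** The entry rule for Cohort 5 is in protocol 5.1, criterion 6: "Completed a full course (two doses) of a COVID-19 mRNA vaccine after start of glatiramer acetate or interferon". The Protocol summary has the same wording ("vaccine after start of glatiramer acetate or interferon"). Criterion 5 adds "Currently on commercially prescribed interferon or glatiramer acetate for" at least 4 weeks, as a description of current status. Criterion 7 asks that the two-dose vaccine was received at least 2 weeks earlier.

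The population that is meant to be analysed is defined differently:

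- Protocol 2.1, population attribute: "Completed a full course (two doses) of a COVID-19 mRNA vaccine after at least 4 weeks of interferon or glatiramer acetate". SAP 1.2.1 and 2.5.1 repeat the 4 weeks.
- Protocol 6.1.3: at least 4 "weeks after glatiramer acetate or interferon start".
- SAP 1.1: "vaccine ≥4 weeks after glatiramer acetate or interferon start".

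The treatment attribute of the same estimand asks only that vaccination took place during interferon or glatiramer acetate treatment, with no interval, so it does not settle the matter.

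The ofatumumab cohorts vaccinated before entry (4 and 6) have the 4 weeks written into their entry criteria. SAP 2.2 defines the Safety Analysis Set as everyone who consented and met the entry criteria. SAP 2.5 uses that set for the primary rate, and SAP 2.1 pools Cohorts 3 and 5.

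**The concern.** The pooled Cohorts 3 and 5 rate is the reference against which the ofatumumab rates will be read. Protocol 1.1 says that MS drugs may weaken vaccine response. Sections 1.1 and 4.3 justify interferon and glatiramer acetate as the reference because a prior study found that they did not. That role depends on participants having been established on those drugs when vaccinated, and the stated population says how long: 4 weeks. The enforceable criterion does not.

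Cohort 3 is protected, since its participants are at least 4 weeks on drug at screening and are vaccinated afterwards. The pooled rate therefore mixes one cohort that satisfies the definition by design with one that need not. Some Cohort 5 participants could also have been vaccinated shortly after stopping another drug, because the wash-out rules were not written around a vaccination that precedes entry.

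**Working it through.** **The plan's own figure.** The plan gives no number for this point. Its only precision figure is the half-width of a 95% interval with 20 participants (protocol 12.8.1, SAP 3). With 1.96 × √(p(1−p)/20):

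- p = 0.70: 20.1 points
- p = 0.75: 19.0 points
- p = 0.80: 17.5 points

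These reproduce, and serve below only as a yardstick.

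**Who can enter under the criteria as written.** Let day 0 be the start of interferon or glatiramer acetate. Criterion 5 puts screening at day 28 or later, criterion 6 puts the second dose after day 0, and criterion 7 puts screening at least 14 days after the second dose. The dose gaps are assumed to follow the protocol's visit schedules: 21 days for Pfizer (Day 1 to 22) and 28 days for Moderna (Day 1 to 29).

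| Reading of criterion 6 | Vaccine | Earliest dose 1 | Earliest dose 2 | Screening possible from |
|---|---|---|---|---|
| Only completion must follow the start | Pfizer | day −20 | day 1 | day 28 |
| Only completion must follow the start | Moderna | day −27 | day 1 | day 28 |
| Both doses must follow the start | Pfizer | day 1 | day 22 | day 36 |
| Both doses must follow the start | Moderna | day 1 | day 29 | day 43 |

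**Comparison with the 4 weeks (28 days).**

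- If the interval runs to the first dose, all four rows fall short.
- If it runs to completion, the first two rows fall short by 27 days. With both doses after the start, Pfizer falls short only when dose 1 is on days 1 to 6 (dose 2 on days 22 to 27), and Moderna always complies.

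The mismatch is therefore widest where the first dose came before interferon or glatiramer acetate was started, and its extent depends on a counting rule that the documents do not give.

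**Previous drugs.** Suppose another drug is stopped on day 0. Take 2 months as 61 days and 6 months as 183 days.

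- Natalizumab: both windows in protocol 5.2 run back from enrollment, so enrollment from day 183 passes whatever the vaccination date.
- S1P agents: exclusion 7 is "Prior treatment with S1P agent within 2 months at Screening", which screening from day 61 passes. The medication table under exclusion 13 also counts 2 months back from the first dose of study drug, a point that is not defined for Cohort 5. If it means the vaccine or the interferon/glatiramer acetate start, this route is closed.
- B-cell-targeted therapies, alemtuzumab, cladribine and the other drugs barred at any time cannot contribute.

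Twenty-eight days is shorter than both 61 and 183. A 4-week rule would leave room for carry-over.

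**Size per participant.** With 22 in the pooled group:

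- One changed outcome moves the rate by 1/22 = 4.5 points.
- Leaving out one participant when k of 22 responded raises the rate by k/462 if a non-responder is dropped, and lowers it by (22−k)/462 if a responder is dropped. Neither exceeds 21/462 = 4.5 points.
- For illustration, at k = 17 (77%), the change is +17/462 = 3.7 points or −5/462 = 1.1 points.

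**The case against.** The strongest reply is that this is a drafting mismatch with little behind it. Several parts of that reply stand.

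- Someone who switched drugs a week before the first dose would complete the course on about day 28 (Pfizer, 7 + 21) or day 35 (Moderna, 7 + 28). If the 4 weeks run to completion, that person meets the definition. A reader might take such a switch as clearly outside the estimand population; the text does not establish that.
- A reader might infer that the missing 4 weeks is what creates carry-over. Any gap comes mainly from where the wash-outs are anchored, and the same anchors apply to Cohorts 4 and 6.
- A reader might infer that the reference rate is pulled down, so that ofatumumab looks closer to control. The documents do not support a direction. Carry-over is also possible in the ofatumumab cohorts, and Cohort 5 may include boosted participants, which could raise its rate.
- The rates are descriptive and no hypothesis is tested. SAP 2.4.1 already summarizes time from the first dose of the most recent MS drug to the first vaccine dose, and SAP 2.4.2 tabulates prior MS drugs, so short intervals would be partly visible.

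None of this removes the mismatch. The SAP attaches no rule to the interval it summarizes, and it plans no subgroup or sensitivity analysis that would separate the participants concerned.

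**Conclusion.** The point holds as a minor inconsistency between eligibility and estimand. Criterion 6 admits participants whom the estimand population and the cohort definitions exclude, criterion 5 does not close the gap, and the analysis set carries those participants into the Cohorts 3 and 5 rate.

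The documents do not say how many there are; there may be none. The ceiling of 4.5 points per participant assumes a group of 22 and is small beside the planned half-widths of 17.5 to 20.1 points. Vaccination soon after another drug is possible for some of them, clearly so for natalizumab and, for S1P agents, depending on how an undefined term is read. No type I error or power is at stake, because nothing is tested. What is affected is whether the reported reference rate describes the population that the plan says it describes.

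**What to change.** Reconcile Cohort 5 criterion 6 (protocol 5.1 and Protocol summary) with protocol 2.1 and 6.1.3 and SAP 1.1, 1.2.1 and 2.5.1. State whether the interval from interferon or glatiramer acetate start runs to the first vaccine dose or to completion of the course. Which rule is right is for the sponsor to decide.

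For participants already enrolled, derive one flag for those who do not meet the reconciled definition. SAP 2.4.1 already yields the interval to the first dose, and the second-dose date is needed as well if the interval runs to completion. Report the Cohorts 3 and 5 response rate, with its exact interval, with and without the flagged participants.

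The cost is one wording change, one flag and one supplementary row. The supplementary rate might lose one or two comparators, though the documents give no basis for a number.

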## 5.2 Exclusion criteria

Participants meeting any of the following criteria are not eligible for inclusion in this study:

1. Already has received the J&J vaccine.
2. Has a contraindication to receiving an mRNA COVID-19 vaccine
3. Has an immediate allergic reaction to past vaccine or injection
4. Any safety finding including low immunoglobulin IgG and/or low immunoglobulin IgM levels requiring an ofatumumab treatment interruption within the 12 weeks immediately prior to vaccination as determined by the HCP
5. Any major episode of infection requiring hospitalization or treatment with intravenous antibiotics within 4 weeks prior to the first vaccination visit or oral antibiotics within two weeks prior to the first vaccination visit
6. Prior treatment with B-cell targeted therapies (e.g., rituximab or ocrelizumab), alemtuzumab, anti-CD4, cladribine, cyclophosphamide, mitoxantrone, azathioprine, mycophenolate mofetil, cyclosporine, methotrexate, total body irradiation, or bone marrow transplantation
7. Prior treatment with S1P agent within 2 months at Screening
8. Prior treatment with natalizumab within 6 months of study enrollment
9. Since commercially prescribed ofatumumab is being used in the study, contraindications as per the USPI will be adhered to which include active infection hepatitis B infection, progressive multifocal leukoencephalopathy and pregnancy.
10. Participation in another interventional clinical trial within 14 days before enrollment.
11. Use of other investigational drugs at the time of enrollment (Screening) or within the prior 30 days, or five elimination half-lives, or until the expected pharmacodynamic effect has returned to baseline, whichever is longer.
12. History of hypersensitivity to any of the study treatments or its excipients or to drugs of similar chemical classes.
13. Have been treated with any of the medications listed below within the time specified:

Medication	Exclusionary if used within the timeframe specified below
Intravenous, oral, intra-articular or intramuscular corticosteroids, adrenocorticotropic hormone	30 days prior to Screening

Medication	Exclusionary if used within the timeframe specified below
Immunosuppressive, chemotherapeutic medications (e.g. mitoxantrone, cyclophosphamide, cladribine, S1P modulators)	2 months prior to first study drug administration
Natalizumab	Within 6 months of study enrollment/Visit 2
Mitoxantrone (with evidence of cardiotoxicity following treatment or cumulative life-time dose > 60mg/m2) Alemtuzumab Lymphoid irradiation; bone marrow transplantation Other strongly immunosuppressive treatments (with effects potentially lasting over 6 months) Ofatumumab aCD20+ monoclonal antibodies in development (e.g. ublituximab or obinutuzumab) Daclizumab	Anytime

14. Women of child-bearing potential, defined as all women physiologically capable of becoming pregnant, **unless** they are using effective methods of contraception while taking study treatment and for 6 months after stopping medication. Effective contraception methods include:

- Total abstinence (when this is in line with the preferred and usual lifestyle of the participant. Periodic abstinence (e.g. calendar, ovulation, symptothermal, post-ovulation methods) and withdrawal are not acceptable methods of contraception.
- Female sterilization (have had surgical bilateral oophorectomy with or without hysterectomy), total hysterectomy, or tubal ligation at least six weeks before taking study treatment. In case of oophorectomy alone, only when the reproductive status of the woman has been confirmed by follow up hormone level assessment.
- Male sterilization (at least 6 months prior to screening). For female participants on the study, the vasectomized male partner should be the sole partner for that participant
- Use of oral, (estrogen and progesterone), injected, or implanted hormonal methods of contraception or placement of an intrauterine device (IUD) or intrauterine system (IUS), or other forms of hormonal contraception that have comparable efficacy (failure rate < 1%), for example hormone vaginal ring or transdermal hormone contraception.
- Barrier methods of contraception: Condom or Occlusive cap (e.g. diaphragm or cervical/vault caps).

In case of use of oral contraception women should have been stable on the same pill for a minimum of 3 months before taking study treatment.

Women are considered post-menopausal and not of childbearing potential if they have had 12 months of natural (spontaneous) amenorrhea with an appropriate clinical profile (e.g., age-appropriate history of vasomotor symptoms) or have had surgical bilateral oophorectomy (with or without hysterectomy), total hysterectomy or bilateral tubal ligation at least six weeks ago. In the case of oophorectomy alone, only when the reproductive status of the woman has been

confirmed by follow up hormone level assessment is she considered not of childbearing potential.

If local regulations deviate from the contraception methods listed above to prevent pregnancy, local regulations apply and will be described in the informed consent form (ICF).

